SynePure Wound Cleanser and Catasyn Advanced Technology Hydrogel demonstrates an improvement in healing, scarring, fibrosis, and infection of burn wounds and complex open wounds. Its toxicity profile, ability to remove biofilms, healing, and anti-inflammatory properties make a compelling case for further testing of SynePure Wound Cleanser and Catasyn Advanced Technology Hydrogel as a new agent to facilitate healing and limit scarring in burn wounds.

3.0 Research Design and Methods:

The study is a prospective, parallel group, randomized controlled trial comparing SynePure Wound Cleanser and Catasyn Advanced Technology Hydrogel (intervention group) to the current gold standard treatment Silvadene (control group). Subjects will be randomized 1:1, either to the treatment group or the standard of care (Silvadene) control group.

Prior to the candidate's referral into the study, as part of standard of care in the burn center, the burn wound is debrided and cleansed in the hydrotherapy area, and then assessed to categorize the burn (superficial, partial thickness,).

Procedural Summary:

- 1. After informed consent process is completed, the study investigator examines and screens the participant to confirm the diagnosis of a superficial-partial thickness burn and all other eligibility inclusion/exclusion criteria. Medical history, medical record review with participant report, medication profile collections, vital signs, demographics, physical exam with burn wound and surface area assessments are completed at this time. Upon completion of these assessments' all findings are reviewed and participant eligibility is determined based on study inclusion and exclusion criteria.
- 2. Should participant be deemed eligible to continue in research; randomization is performed to determine group assignment with randomization to either the intervention group (SynePure Wound Cleanser and Catasyn Advanced Technology Hydrogel) or the control group (Silvadene). Prior to application of treatment agent and dressing application, 2D photographs will be taken of the burn area for later evaluation.
- 3. During the Initial treatment visit (Day 0), after randomization, the treatment agent is applied (SynePure Wound Cleanser and Catasyn Advanced Technology Hydrogel or Silvadene) to complete secondary dressing with a dry gauze and Kerlix wrap application.

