Descriptive statistics will be presented as means and standard deviations for continuous data and as counts and percentages for dichotomous and categorical data. Time-to-event curves with Kaplan-Meier (KM) estimates will be used to compare overall median time to wound healing between treatment groups. Comparison of KM curves will be performed using the log rank test as the curve is assumed to be non-parametric or semi-parametric, and the baseline hazard is not related to the group assignment. Relevant clinical and demographic variables may be assessed for their independent contribution in time-to-event outcome using univariate screening and the hazard is assumed to be relatively constant across the study window. Multiple regression modeling (Cox Proportional Modeling) and adjusted KM curves will be assessed as appropriate. Variables will be included in the multivariate analysis if the univariate screening p-value is < 0.10 and multivariate parameters will be presented as hazard ratios with their corresponding 95% confidence intervals.

Infection, complication, and progression rates will be compared using the Chi-squared test or the Fisher exact test if the data is very unequally distributed within the contingency table, which is anticipated for infection rates. Repeated Measure Analysis of Variance (ANOVAs) will be performed to assess differences in PROs with the days since wounding as the Within-Subjects factor and treatment groups as the Between-Subjects factors. Bonferroni post-hoc analyses may be performed for all statistically significant main effects. Baseline demographic and clinical characteristics will be compared between treatment groups with Independent samples t-test for continuous data and Chi-squared test for dichotomous and categorical data.

Analysis will be performed using SPSS (IBM SPSS Statistics for Windows, Version 25.0. Armonk, NY: IBM Corp.) and statistical significance will be determined at $p \le 0.05$ with the exception of univariate screening as previously described.

Outcome definitions:

- 1. Healed wound: 90% reepithelialization (skin and mucous membrane replacement) of the wounded area.
- 2. Infection: characterized by local new inflammation, heat, purulence as well as new or increased pain, redness and swelling
- 3. Complications other than infection: gangrene, necrosis, periwound dermatisis and/or edema, hematoma, or any other complication determined to be related to the wound and/or treatment

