4. Progression; recategorization of the wound to a more advanced state deep partial thickness, full thickness. Failure to heal with 21 days of injury also may be determined as progression by the investigator.

4.0 Human Subjects:

4.1 General Characteristics:

Inclusion criteria:

- 18 years of age or older, Male and Female
- Ability to provide informed consent
- Patients who have sustained superficial, partial thickness burn wounds ≤ to10% of total body surface area (TBSA)
- Patients otherwise in good general physical and mental health, as per the investigator's clinical judgment

Exclusion criteria:

- Inability to provide informed consent
- Deep partial-thickness burns and full-thickness burns
- Radiation, chemical or electrical burn injury
- Patients with burns primarily located to the face, genitals, or span across joints
- Patients whose burn injury was ≥ to 48 hours prior to entry into the UPMC Mercy Burn Clinic.
- Patients with uncontrolled cerebrovascular disease, cardiovascular disease, concurrent endocrine, hepatic or renal disease, or other severe conditions for whom, in the investigators' discretion would render study participation unsafe
- Current pregnancy
- Patients with concurrent burn related injuries or inhalation injury that would put the patient at increased risk, per physician discretion
- Any condition to which in the investigator's discretion would render study enrollment a safety concern for the patient.

All patients who present to the UPMC Mercy ER or Burn Center, whose burns are assessed to be superficial, partial thickness burns, and who also meet the study's eligibility criteria in the opinion of the referring physician will be considered for participation.

The racial, gender and ethnic characteristics of the proposed subject population reflects the demographics of Pittsburgh and the surrounding area and/or the patient population of the University of Pittsburgh Medical Center. We shall attempt to recruit subjects in respective proportion to these demographics. No exclusion criteria shall be based on race, ethnicity, gender, or HIV status.

The study will plan to enroll 115 subjects in order to randomize 100 subjects, to either the intervention group (SynePure Wound Cleanser and Catasyn Advanced Technology Hydrogel) or the control group (Silvadene). It is expected that some subjects will not meet screening criteria after they are consented, and will therefore not proceed forward to randomization.

4.4 Recruitment Procedures:

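### The only committed test of healing time is an unadjusted log-rank test; naming burn size and age in that test could recover power if they are prognostic, at small cost

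*Combined protocol and SAP*

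**What the plan says.** Section 3.1, Analytic Plan, compares median healing time with Kaplan-Meier estimates and states: "Comparison of KM curves will be performed using the log rank test". It gives no strata and no covariates for that test.

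Adjustment appears in the same paragraph, but only as a possibility. "Relevant clinical and demographic variables may be assessed for their independent contribution in time-to-event outcome using univariate screening", and then: "Multiple regression modeling (Cox Proportional Modeling) and adjusted KM curves will be assessed as appropriate". Entry to the model depends on the data: "Variables will be included in the multivariate analysis if the univariate screening p-value is < 0.10". No candidate variable is named.

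Section 3.0, Procedural Summary, step 1 places the relevant measurements at screening: "demographics, physical exam with burn wound and surface area assessments are completed at this time". Randomization follows in step 2. Age is not listed by name, but it is part of demographics and is needed for the adult age criterion in section 4.1.

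Section 4.1 admits "Patients who have sustained superficial, partial thickness burn wounds" up to 10% TBSA and sets no upper age limit. In the text available for review, randomization is described only as a predefined 1:1 scheme, with no stratification factor.

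**The concern.** Healing time is the subject of the first specific aim and the outcome on which the sample size rests. Patients can differ in burn size and age, and both are known before allocation. If either is related to healing, an unadjusted log-rank test leaves that explainable variation in the comparison. It then has less power than a test that conditions on it.

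The Cox model in the plan does not secure the gain, because it is neither committed nor the deciding analysis. At stake is power in a small trial, and a clear answer to which of two healing results, unadjusted or screened-adjusted, is the result of record.

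**Working it through.** **The plan's own setting.** Section 3.1, Sample Size Estimation, gives a control median of 15 days, a 3-day difference, a hazard ratio of 0.8, 45 per group, 80% power and alpha 0.05. Sidedness is not stated, so two-sided is assumed. The follow-up is 3 weeks. The 0.8 is the ratio of medians, 12/15; as a hazard of healing it is 15/12 = 1.25.

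- Events needed (Schoenfeld): 4 × (1.960 + 0.842)² / (ln 0.8)² = 631. The stated 90 patients do not reproduce.
- Healed by day 21 under exponential times: 1 − 2^(−21/12) = 70% and 1 − 2^(−21/15) = 62%. Expected events: 45 × (0.703 + 0.621) = 59.6.
- Power with 59.6 events: Φ(½ × √59.6 × 0.223 − 1.960) = Φ(−1.10) = about 14%. If all 90 healed it would be 18%.
- Hazard ratio at which 90 events give 80% power: exp(−2 × 2.802 / √90) = 0.554, or 1/0.554 = 1.8 as a healing hazard. This is why 1.8 serves as the second effect size below. It is not a figure from the protocol.

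**Simulation.** Patient i heals at rate λ₀ × HR^g × exp(σZ), where g is the arm and Z is a standard normal prognostic score standing for burn size and age together. λ₀ is set so that the marginal control median is 15 days. Times are censored at day 21, with 45 per arm. The unadjusted log-rank test is compared with the treatment term in a Cox model that always contains the covariates. The documents give no prognostic strength, so σ is an assumption and is varied. With 3,000 trials per setting the simulation error is at most about √(0.5 × 0.5 / 3,000) = 0.9 point. Ranges show the spread over repeated runs.

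Power at a conditional hazard ratio of 1.8:

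| σ (assumed) | Log-rank | Adjusted Cox | Difference |
|---|---|---|---|
| 0 | 66% | 65% | −1 |
| 0.35 | 59–61% | 63–64% | about +3 |
| 0.7 | 47–48% | 61–63% | about +15 |
| 1.0 | 37–39% | 59–61% | about +22 |

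Power at the plan's own effect, hazard ratio 1.25 (10,000 trials per setting):

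| σ (assumed) | Log-rank | Adjusted Cox | Difference |
|---|---|---|---|
| 0 | 13.6% | 13.8% | +0.2 |
| 0.5 | 11.8% | 13.7% | +1.9 |
| 1.0 | 9.4% | 12.8% | +3.4 |

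**Error rate.** With no treatment effect, the adjusted test rejected in 4.5% to 5.9% of trials and the log-rank test in 4.6% to 5.7%.

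**The plan's optional model.** With the p < 0.10 screen applied to both covariates at hazard ratio 1.8, power for log-rank / prespecified Cox / screened Cox was 59% / 64% / 62% (σ 0.35), 48% / 62% / 62% (σ 0.7) and 38% / 59% / 59% (σ 1.0).

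**The case against.** The strongest reply is that nothing here is an error. The log-rank test is valid under randomization and holds its level. It also matches the plan's stated interest in overall medians, which is a marginal comparison. Four further points have weight.

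- **Strength of the covariates.** No passage says that burn size or age predicts healing. A σ of 0.7 or 1.0 implies a healing hazard exp(4 × 0.7) = 16 or exp(4 × 1.0) = 55 times higher at +2 SD than at −2 SD. Eligibility is narrow: at most 10% TBSA, deep burns excluded, good general health. Healing is defined as a proportion of the wound, which may weaken its dependence on size. This stands; the documents do not favour the larger gains over the smallest.
- **An idealised simulation.** It gives the Cox model the correct covariate form and healing times observed continuously. Assessment at clinic visits and a misspecified form could yield less. This stands.
- **Adjustment is already foreseen.** If the screened Cox model were run with these two candidates, it would recover nearly all of the gain. That is true, but the plan does not commit to running it, does not name the candidates and does not make it the deciding test.
- **Bias.** A reader might infer that the unadjusted hazard ratio is wrongly diluted toward 1. It is not biased. Marginal and conditional hazard ratios are different quantities, and the plan's target is marginal.

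**Conclusion.** The point holds as a cheap improvement, not as a flaw that invalidates the analysis. The committed healing test ignores baseline data that the trial already collects, and the optional model does not close that gap. If burn size and age are prognostic, about 3 to 22 points of power may be forgone at a conditional hazard ratio of 1.8. If they are not, adjusting costs about 1 point or less. These figures rest on an assumed σ, exponential healing times, a two-sided 5% level, continuous observation to day 21 and a correctly specified covariate effect.

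Three stronger readings are not supported. The documents do not show that the plan does lose power, because they give no prognostic strength. The change is not free, because the estimand shifts and the test comes to depend on a model. Nor would adjustment rescue the trial: at the plan's own effect it adds 0 to about 3.5 points and leaves power near 10% to 14%. The shortfall there is in events, 631 needed against about 60 expected.

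**What to change.** Before any outcome data are seen, amend the Analytic Plan along these lines: the test of record for time to healing is the treatment term in a Cox model containing treatment, log percent TBSA and age, both covariates retained whatever their p-values, at two-sided 0.05. A log-rank test stratified by a TBSA cut fixed in advance is an acceptable alternative that relies less on the covariate's form. Drop p-value screening for this comparison; it may remain for exploratory work on predictors of healing. Keep the unadjusted Kaplan-Meier medians and log-rank test as supporting results, so that the marginal comparison is still reported.

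The cost is plan wording only. Burn area and demographics are already collected at screening, though the case report form should be checked to confirm that percent TBSA is recorded as a number. The downsides are small: the hazard ratio becomes conditional on burn size and age, and the test relies on proportional hazards and the chosen covariate form. The sample size needs its own correction, separate from this change.

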POSAS: The patient and observer scar assessment scale¹⁵⁻¹⁶ is used to measure scar quality. It is composed of a patient reported section and an observer reported section. Each section consists of six items that are scored numerically on a ten-step scale. These are then summed together to make up the total score. There is also an overall opinion section for both the patient and the observer. While validity and reliability are marginal for the POSAS, scores have shown little variance from the gold standard, the Vancouver Scar Scale, and it has the distinct advantage of incorporating the patient's perspective.

Wound Experience Questionnaire: The wound experience questionnaire ¹⁷ consists of three sections regarding the patient's wound. The questionnaire is used for wounds early into the healing process and wounds that have dressings. This has been primary used in patients with surgical wounds but can be adapted to wounds not specifically operative, such as burns. Validity and reliability evidence have not been published but the questionnaire has the unique capability to assess a primary focus of this study. In addition to assessing patient satisfaction with the healing process, the questionnaire also assesses patient satisfaction with the wound dressings as distinct categories.

3.1 Data Collection and Statistical Consideration:

Sample Size Estimation:

In this study, the minimal median difference of three (3) days to healing is determined to be the clinically relevant difference. Given an assumed median time of 15 days to healing for the Silvadene comparator group 18 , a corresponding hazard ratio of 0.8 for the intervention group is anticipated. a sample of 45 in each group (90 total) is required to detect a statistically significant difference [confidence level ($\alpha \leq 0.05) - 95\%$; Power - 80%]. Assuming a 10% attrition, it is recommended to enroll up to 100 subjects to achieve a sample of 90 subjects. This will be easily accomplished in our outpatient burn clinic, with a 400-patient annual volume, and we will use a 3-week evaluation period so that the trial can be accomplished in a year.

Analytic Plan:

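### Does the plan leave the healing comparison without a confidence interval by promising hazard ratios only for an optional Cox model?

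*Combined protocol and SAP*

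**What the plan says.** All of this is in section 3.1 of the combined protocol and SAP.

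- **Analytic Plan, committed part.** Kaplan-Meier estimates "will be used to compare overall median time to wound healing between treatment groups". The test is also fixed: "Comparison of KM curves will be performed using the log rank test".
- **Analytic Plan, conditional part.** "Multiple regression modeling (Cox Proportional Modeling) and adjusted KM curves will be assessed as appropriate". The entry rule is "Variables will be included in the multivariate analysis if the univariate screening p-value is < 0.10", and the screening is itself described as something that may be done. Hazard ratios with intervals are named only here: "multivariate parameters will be presented as hazard ratios with their corresponding 95% confidence intervals".
- **Sample Size Estimation.** The target is stated in days, "the minimal median difference of three (3) days to healing is determined to be the clinically relevant difference", and then as a hazard ratio of 0.8 for the intervention group. The base is "Given an assumed median time of 15 days to healing for the Silvadene comparator group".

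The text available for review does not name an unadjusted hazard ratio, an interval for one, or an interval for the medians or their difference. Some pages before the reference list were not available, so the absence is established only for the text seen.

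**The concern.** The trial is sized on an effect, but the analysis it commits to yields two medians and a p-value. If the Cox model is not run, no promised output says how large or small the healing effect could be. If it is run, the interval belongs to a covariate-adjusted effect from a model whose contents depend on the data. The plan does not say that treatment is kept in that model.

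What would be at stake is interpretation. With 90 patients, a chance difference in medians could be taken for the 3-day benefit, or a non-significant p-value could be taken to show that the benefit is absent. An interval guards against the second misreading.

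**Working it through.** **Inputs.** From Sample Size Estimation: control median 15 days, difference 3 days, hazard ratio 0.8, 45 per arm, 10% attrition, 3-week evaluation period (taken as follow-up to day 21). From the Analytic Plan: significance at 0.05 (two-sided assumed, since sidedness is not stated), and "the hazard is assumed to be relatively constant across the study window", which supports exponential healing times. Healing times are treated as observed exactly.

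**The plan's own figures.** 15 − 3 = 12 days, and 12/15 = 0.8. Attrition: 90/(1 − 0.10) = 100. Both reproduce. The 45 per arm does not: 4 × (1.96 + 0.842)² / (ln 0.8)² gives 631 events. That is a separate matter.

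With healing as the event, constant hazards and medians of 12 and 15 days, the intervention-to-control hazard ratio is 15/12 = 1.25, the inverse of 0.8. The calculations below use 1.25.

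**1. How often do medians differ by 3 days by chance?**
- Standard error of one median: 15/(ln 2 × √45) = 3.23 days.
- Standard error of the gap: 3.23 × √2 = 4.56 days. So P(|gap| ≥ 3) is about 51%.
- Simulation with the day-21 cut-off: 46.5% of trials in which both medians are reached, which is 90.5% of trials.
- With a rising hazard the figure falls to 18.6% (Weibull shape 2) or 4.8% (shape 3).

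**2. Is the reader misled by that gap?** The plan reports the log-rank result beside the medians. In no-effect simulations on the same model, 93.6% of trials with a gap of 3 days or more have a non-significant log-rank test. A gap of that size with p < 0.05 occurs in 0.905 × 0.465 × 0.064 = 2.7% of all no-effect trials.

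**3. What would the interval show?**
- No effect: events by day 21 = 90 × (1 − 2^(−21/15)) = 55.9. SE of the log hazard ratio = 2/√55.9 = 0.268. Factor = exp(1.96 × 0.268) = 1.69. The 95% interval around 1.0 is 0.59 to 1.69.
- At medians 15 and 12: proportions healed are 0.621 and 0.703, so events = 90 × 0.662 = 59.6. The factor is exp(1.96 × 2/√59.6) = 1.66. The interval around 1.25 is 0.75 to 2.08.

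In simulation at hazard ratio 1.25, the treatment-only interval and the log-rank test disagree on significance in only 0.4 to 0.6% of trials. The interval therefore describes the committed comparison without competing with it.

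**4. Would intervals for each median fill the gap?** Often not. Under the same exponential model, the control median has no upper 95% limit by day 21 in 57% of trials. At least one arm lacks one in 81% of no-effect trials.

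**5. Does the conditional Cox model threaten validity?** With 8 assumed baseline candidates and treatment kept in, the screened model rejects in 4.9 to 5.5% of no-effect trials. Screening baseline covariates does not inflate the error rate materially. At hazard ratio 1.25 its interval disagrees with the log-rank test in 2.0 to 10.6% of trials, but that range rests on assumed numbers of covariates (4 to 15) and assumed strengths that the documents do not give.

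**The case for a change.** The best case for a change is that the remedy is nearly free and the trial especially needs it. Under constant hazards, log-rank power at hazard ratio 1.25 is about 14%, so about 86% of trials at the plan's own effect end with p > 0.05. In about 97% of those, a treatment-only interval still contains 1.25. A bare p-value would hide that the benefit remains open. Leaving the interval to the analyst's good sense is weaker than writing it down, and the one interval the plan names comes from a different model.

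Part of this stands. The omission is real, and an interval is the right companion to a non-significant test here. The direction of the hazard ratio also has to be stated when it is reported, because a healing hazard ratio of 1.25 could otherwise be read against the protocol's 0.8 the wrong way round.

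The rest is weaker. The 86% is the sample-size shortfall under another name and depends on hazard shape: for the same 15 versus 12 days, power is about 14%, 48% and 85% at Weibull shapes 1, 2 and 3. Disagreement between the two models matters only if they rank equally, and the plan does not rank them so: the log-rank test will be done, while the Cox model is conditional and serves to examine the contribution of other variables.

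**Conclusion.** No change to the plan follows. This is an unwritten reporting item that a competent analyst fills in as a matter of course. The Sample Size Estimation already expresses the effect as a hazard ratio, nothing in the Analytic Plan forbids an unadjusted one, and a treatment-only model leaves no choice of covariates. It needs no further patients, visits, data or alpha, and can be given whatever the p-value. Without it, the Kaplan-Meier and log-rank comparison remains valid and its conclusion sound.

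The risk of taking a chance 3-day gap for a real effect is about 2.7% of no-effect trials once the p-value is read with the medians, not the 46.5% that the medians alone suggest. Both figures assume constant hazards, 45 per arm, a 15-day median and follow-up to day 21. The expected width of the interval (a factor of about 1.66 to 1.69 either way) comes from the number of events, and wording in the Analytic Plan would not narrow it.
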